Information-based interventions typically rely on people being motivated by health in their food choices [16]. Yet, health may be a less influential motive for food choice among people of lower SEP [17]. Thus, SEP based differences in food choice motives, and notably health motivation, may explain why information-based interventions could be less effective among people of lower vs. higher SEP.

The aim of this study is to examine how an information-based intervention (labelling of lower ED food products) and a structural intervention (greater proportion of lower ED options in food product ranges) affect the ED of food purchases within a virtual online supermarket [18] in participants of lower vs. higher SEP. The primary hypothesis is that labelling will reduce the ED of virtual online supermarket food purchases to a greater extent in participants of higher SEP vs. lower SEP. Conversely, we hypothesise that a greater proportion of lower ED options will decrease the ED of food purchases equally among participants of lower and higher SEP. The secondary hypothesis is that differences in health-based food choice motives in participants of lower vs. higher SEP will mediate the differential effect that ED labelling has on ED of food purchases among participants of lower vs. higher SEP.

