## 2. OBJECTIVES, OUTCOMES MEASURES AND HYPOTHESES

OBJECTIVES	OUTCOME MEASURES	HYPOTHESES
Primary objective		

To examine the effectiveness of an information-based intervention (ED labelling) and a structural nutrition intervention (greater proportion of lower ED options) on the ED of virtual online supermarket food purchases; and if this effect is different between participants of lower and higher SEP.	Mean ED (kcal/100g) of foods purchased	SEP will influence the effect of the interventions. In particular, ED labelling will reduce ED of foods purchased to a greater extent in participants of higher vs. lower SEP. Conversely, a greater proportion of lower ED options will decrease ED of food purchases equally among participants of lower and higher SEP.
Secondary objectives  To investigate the psychological processes that explain why an information-based intervention (ED labelling) and a structural nutrition intervention (greater proportion of lower ED options) may have differential effects on ED of food purchases among participants of lower vs. higher SEP.	Health and weight control food choices motives (questionnaire score)	The participants of higher SEP will be more motivated by health and weight control in their food choices than participants of lower SEP, which will moderate the relationship between SEP and the effect of ED labelling on ED of foods purchased.

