#### 7.5. Primary analyses

The measure of SEP used in our primary analysis will be the *level of education* because previous research showed that people of higher education were more likely to use nutrition labels [32], [33].

**ANCOVA** will be used to test the effect of *labelling* (categorical variable: yes or no), *proportion* (categorical variable: default or increased), *level of education* (continuous variable) and *labelling\*level of education* and *proportion\*level of education* interactions on the *mean ED of foods purchased*. If this analysis reveals the predicted significant interaction between *labelling* or *proportion* condition and the continuous measure of *level of education* on *mean ED*, we will further examine the nature of the interactions by conducting floodlight analysis [34]. We will calculate the Johnson–Neyman point defined as the value of *educational level* for which the effect of *labelling* (or *proportion*) reaches statistical significance [35]. Values of *level of education* above this point will correspond to significant differences between the *labelling* and *no labelling* conditions (resp. the *default* and increased *proportion* conditions) whereas values below the point will not. The floodlight analysis will be run using the SAS macro developed by Hayes & Matthes, 2009 [36].

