## 7.7. Secondary analyses

### Moderated mediation analysis

[figure not shown]
We will describe health and weight control motivation in the overall sample using mean and standard deviation and report the correlation (Pearson's) between the health and weight control motivation scores and level of education.

If the primary analyses suggest that *level of education* moderates the effect of *labelling* or *proportion* on the *mean ED of foods purchased* (i.e., the *labelling\*level of education* or *proportion\*level of education* interaction is significant), mediation analyses will be performed in order to examine the extent to which 1/ health food choice motive, 2/ weight control food choice motive mediates the effect of *level of education* on the *mean ED*.

Conceptual diagram example (labelling):

Statistical diagram example (labelling):

Conditional indirect effect of *level of education* on the *mean ED* through a mediator (M) =  $a(b_1 + b_2 \text{labelling})$ .

The moderated mediation will be tested by estimating the conditional indirect effect of *level of education* on the *mean ED* through M for *labelling* and *no labelling* conditions (resp. the *default* and *increased proportion* conditions) and testing the conditional indirect effect for those conditions using bias-corrected bootstrap. We will use the PROCESS macro (Model 15) on SAS software that provides asymmetric bias-corrected bootstrap confidence intervals for inference about the conditional indirect effects using 5,000 bootstrap samples [37]. Moderated mediation will be tested by determining whether or not the confidence interval for the difference between conditional indirect effects for *labelling* vs. *no labelling* conditions (resp. the *increased* and *baseline availability* conditions) contains zero.

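### The floodlight rule in Section 7.5 places significance above a single Johnson-Neyman point for proportion as well as labelling, so it reads backwards if the proportion effect is larger at lower education

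*Combined protocol and SAP*

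**What the plan says.** Section 7.5 fits an ANCOVA with labelling, proportion, level of education (continuous) and the two intervention-by-education interactions. The follow-up begins "If this analysis reveals the predicted significant interaction between" either intervention and education. It names one Johnson-Neyman "point defined as the value of" education at which the intervention effect becomes significant. It then fixes the reading: values "above this point will correspond to significant differences between the" labelling conditions, "whereas values below the point will not". A bracket carries the same reading over to default versus increased proportion. A SAS macro does the computation.

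The hypotheses differ between the two interventions. For labelling, Section 2 states that "ED labelling will reduce ED of foods purchased to a greater extent in participants of higher vs. lower SEP". For proportion, it states that "a greater proportion of lower ED options will decrease ED of food purchases equally among participants of lower and higher SEP", and Section 1 says the same. Section 2 also opens with a general remark that socioeconomic position will influence the interventions' effects, but that remark gives no direction. No section says how to read an interaction that runs the other way, or what to do when two boundaries or none fall within the data.

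**The concern.** Which side of a Johnson-Neyman boundary is significant depends on the fitted coefficients and cannot be fixed beforehand. For labelling, "above" follows from the stated hypothesis. For proportion, no interaction is predicted, so both the word "predicted" in the trigger and "above" in the reading lack a basis. If increased proportion lowers energy density more at lower education, the significant region lies below the boundary, which reverses the sentence.

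There is a second, smaller fault. After a significant interaction there are always two boundaries on the unbounded education scale, with significance outside both. If the lower one falls within the data, a one-point rule labels as no difference a low-education region where the effect is significant and of opposite sign. For labelling, that would be a significant increase in energy density.

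This step tells readers at which education levels each intervention works, which is part of the primary objective. An inverted reading names the wrong group as benefiting.

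**Working it through.** **Inputs from the plan.** Section 7.8: n=788 (197 per group), main effects and interactions of f=0.1, 80% power. Section 7: alpha 0.05. Section 7.8 also cites f=0.14 and f=0.04 for the energy-density effects of two interventions in an earlier study; these serve as alternative main effects.

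**Assumptions.** Residual SD 1 and education standardised. The documents do not give the education distribution, so simulation results are shown as normal / discrete. The discrete version has nine qualification levels with 60% in the lowest four and years of education floored at 0; it averages the two z-scores.

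**The plan's own figure.** Noncentral F with df1=1, df2=788−5=783 and λ=0.1²×788=7.88 gives power 0.8006. The minimum n is 787, or 788 in four equal groups. The stated sample size reproduces.

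**Why there are two boundaries.** Write the intervention effect at education x as t0+t1·x. The boundaries solve

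(t0+t1·x)² − tcrit²·Var(t0+t1·x) = 0.

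The coefficient of x² is t1² − tcrit²·Var(t1), which is positive exactly when the interaction is significant at the same alpha. At x=−t0/t1 the left side is negative. Hence there are two real roots, with significance outside them and the sign change between them.

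**Boundaries by hand.** With two equal halves, f=0.1 is a difference of 0.2 SD; with education at SD 1, an interaction of f=0.1 is a slope of 0.2 in size. SE=2/√788=0.0712 and tcrit=1.963, so tcrit²·SE²=0.01956 and Var(t0+t1·x)=SE²(1+x²). For t0=−0.2, t1=+0.2:

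(0.04−0.01956)x² − 0.08x + (0.04−0.01956) = 0, giving x=0.27 and 3.64.

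| Main effect t0 | Slope t1 | Boundaries (SD) | Significant within ±2 SD |
|---|---|---|---|
| −0.2 | −0.2 (larger at higher education) | −3.64, −0.27 | above −0.27: rule correct |
| −0.2 | +0.2 (larger at lower education) | 0.27, 3.64 | below 0.27: rule reversed |
| −0.28 (f=0.14) | +0.2 | 0.59, 4.89 | below 0.59: rule reversed |
| 0 | +0.2 | −0.98, 0.98 | both outer sides: one point insufficient |

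In the second row, 61% of a normal sample lies below 0.27 and 0.01% above 3.64.

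**Simulation of the planned ANCOVA.** There were 4,000 trials per scenario and 30,000 with no interaction. Except where noted, shares are of trials with a significant interaction.

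| Scenario | Result | Normal / discrete |
|---|---|---|
| Labelling as predicted, main f=0.1 | only upper boundary within ±2 SD | 71% / 70% |
| | over 5% of participants significant below the lower boundary | 18% / 8% |
| Labelling as predicted, main f=0.04 | over 5% of participants in both outer regions | 53% / 37% |
| Larger at lower education, main f=0.1 | only lower boundary within ±2 SD | 69% / 70% |
| | median share of participants below it | 59% / 63% |
| Larger at lower education, main f=0.14 | only lower boundary within ±2 SD | 85% / 86% |
| No true interaction, main f=0.1 | significant interaction, of all trials | about 5% |
| | of those, larger at lower education | 49% / 51% |
| | of those reversed, only lower boundary within ±2 SD | 98% / 96% |

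**Separate check, normal education.** With the effect larger at lower education and main f=0.1, 3,232 of 4,000 trials had a significant interaction. Within ±2 SD, 2,273 of these (70%) were significant only below the boundary, 958 (30%) had two boundaries, and none was significant only above. With main f=0.14, 2,672 of 3,141 (85%) were significant only below and none only above. With main f=0.14 and no interaction, 190 of 4,000 (4.8%) were significant by chance: 94 only above and 96 only below.

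**The case against.** The strongest reply is that the sentence explains the method and does not override the output. The macro works from the fitted model, so a reversed interaction would show in its coefficient and in the conditional effects; analysts would have to report against their own results to name the wrong group. The binary-education analysis in Section 7.6 could also expose the direction. This limits the likely harm, but the sentence is worded as the reading rule and expressly includes proportion. Correct output would contradict the plan and force an unplanned departure from it.

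Second, the large percentages assume a true reversed proportion interaction, which the plan does not expect. Under its own hypothesis the reversal arises in about 5% × one half, or roughly 2.5% of all trials. That is fair, but the step is planned precisely for a significant interaction.

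Third, the two-boundary problem for labelling is weaker. At main f=0.1 the expected lower boundary is −3.64 SD, so it enters the data only through sampling variation. The f=0.04 figures borrow the effect of a different intervention. For a skewed composite, ±2 SD also exceeds the observed range: in another assumed discrete version the minimum was about −1.6 SD, and the lower boundary fell within the data in about 17% of significant trials. This stands as a limit on the labelling part; it does not touch proportion.

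**Conclusion.** The reading rule is wrong as written and should be corrected. It covers proportion, no direction is predicted for proportion, and it inverts the conclusion when the proportion effect is larger at lower education. The inversion depends only on the sign of the interaction relative to the main effect. The percentages depend on the assumed effect sizes and education distribution.

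In the reversed case at f=0.1, a median of about 60% of participants would be placed on the wrong side. For labelling in its predicted direction the rule usually reads correctly, with a smaller risk of hiding a low-education region of opposite sign.

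The fault matters only after a significant interaction. The ANCOVA, the interaction tests and the sample size are unaffected. So is the decision to run the mediation analysis in Section 7.7, which depends on whether an interaction is significant and not on any region.

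**What to change.** Replace the above/below sentence in Section 7.5 with:

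*For any significant interaction, whatever its direction, report every Johnson-Neyman boundary within the observed range of level of education and, for each region, the sign of the effect, whether it is significant, and the share of participants in it.*

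Make no assumption that significance lies above the boundary, and keep the word "predicted" for the labelling interaction only. The share of participants is not strictly needed to cure the fault, but it shows readers how many people each statement covers.

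The cost is one SAP sentence and the limit on one word, with no new data and no new analysis.

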#### 7.6. Sensitivity analyses

Sensitivity analyses will be conducted to examine whether the pattern of results from the primary analyses differ after excluding participants guessing the aims of the study.

We will repeat our main analyses with a more stringent criteria for having completed the shopping task as intended (excluding any participants who did not select 10 items in total and 1 item from each category on the shopping list).

We will also repeat the main analysis substituting the composite variable *level of education* by *years in higher education* as a continuous covariate (ANCOVA) and by *highest educational qualification* split into lower vs. higher qualification levels as a binary covariate (2x2x2 ANOVA).

We will report whether sensitivity analyses result in deviations from the pattern of significance to the main analyses (i.e., any significant differences between conditions becoming not significant, and vice versa).

[figure not shown]

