### 4. PARTICIPANTS AND RECRUITMENT

#### 4.1. Recruitment

Participants will be recruited through an online recruitment panel (Prolific) in which participants are compensated proportionate to the time it takes to complete the online study ( $\approx$  £5/hour reward participants).

Participants' recruitment will be stratified by gender (50% male, 50% female), student status (3.5% yes and 96.5% no) [19] and qualification levels; the proportion of low (below level 4) versus high (level 4 or above) qualification levels will be based on current population statistics from the Labour Force Survey (LFS) 2013 for adults aged 19-64 in England [20]:

- **60% lower qualification levels**
  - No formal qualifications
  - 1–3 GCSEs or equivalent

*(Level 1: first certificate; GCSE - grades 3, 2, 1 or grades D, E, F, G; level 1 award; level 1 certificate; level 1 diploma; level 1 ESOL; level 1 essential skills; level 1 functional skills; level 1 national vocational qualification (NVQ); music grades 1, 2 and 3)*

- 4+ GCSEs or equivalent

*(Level 2: CSE - grade 1; GCSE - grades 9, 8, 7, 6, 5, 4 or grades A\*, A, B, C; intermediate apprenticeship; level 2 award; level 2 certificate; level 2 diploma; level 2 ESOL; level 2 essential skills; level 2 functional skills; level 2 national certificate; level 2 national diploma, level 2 NVQ; music grades 4 and 5; O level - grade A, B or C)*

- A level or equivalent

*(Level 3: A level; access to higher education diploma; advanced apprenticeship; applied general; AS level; international Baccalaureate diploma; level 3 award; level 3 certificate; level 3 diploma; level 3 ESOL; level 3 national certificate; level 3 national diploma; level 3 NVQ; music grades 6, 7 and 8; tech level)*

- **40% higher qualification levels**

- Certificate of higher education (CertHE) or equivalent

*(Level 4: certificate of higher education (CertHE); higher apprenticeship; higher national certificate (HNC); level 4 award; level 4 certificate; level 4 diploma; level 4 NVQ);*

- Diploma of higher education (DipHE) or equivalent

*(Level 5: diploma of higher education (DipHE); foundation degree; higher national diploma (HND); level 5 award; level 5 certificate; level 5 diploma; level 5 NVQ)*

- Bachelor or equivalent

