### Analyses of secondary outcomes

For descriptive purposes we will code each participant product selection based on the food categories outlined in the shopping list and repeat the primary analysis strategy on each of the 10 food categories individually.

To further investigate the effect of the interventions and level of education, we will repeat the primary analysis strategy with the following dependent variables:

- on total energy of the foods purchased;
- on energy from total sugar;
- on energy from SFA;
- on salt content;

- on proportion of lower ED foods in the basket of foods purchased;
- on cost of the foods purchased.

We will also repeat the primary analysis including the interaction between labelling and proportion in the model.

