## APPENDIX A: AUDIENCE (PROLIFIC WEBSITE)

### 1. Age

- 18 years old or over

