#### 2. Age

- \_\_ (free text; range of 18-99)

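### Does the absence of any model with age undermine the planned tests of whether labelling and proportion effects differ by education?

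*Combined protocol and SAP*

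**What the plan says.** Section 7.5 fits an ANCOVA of mean energy density on labelling, proportion, a continuous education score, and the products of that score with each intervention. Section 7.6 excludes participants who guess the aim, tightens the definition of task completion, or changes the education measure: "We will also repeat the main analysis substituting the composite variable" by years in higher education or by a binary qualification variable. Section 7.7 adds mediation through health and weight-control motives, conditional on a significant primary interaction, and one further model: "We will also repeat the primary analysis including the interaction between labelling and proportion in the model".

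Age appears in none of these models. In the recruitment plan (4.1), "recruitment will be stratified by gender (50% male, 50% female), student status" and qualification level are fixed, while Appendix A sets age only at "18 years old or over". The baseline questionnaire in Appendix E accepts age as "free text; range of 18-99". Beyond eligibility, the only stated use of age is the baseline table by condition (7.2).

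The primary objective in section 2 is whether the interventions work and whether their effect differs between lower and higher SEP. The matching hypothesis opens with "SEP will influence the effect of the interventions".

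**The concern.** Randomisation protects the labelling and proportion main effects. It does not protect the interpretation of an interaction with education, which is not randomised. If age changes how people respond to a badge or to a different product range, and age is related to education in the panel, the education product term absorbs part of the age effect. Swapping one education measure for another cannot separate the two.

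Age looks like the natural candidate. Unlike BMI or dieting it cannot be a consequence of education, and unlike income or subjective status it is not itself a measure of SEP. The data are in hand, and one model with three more terms would address it. At stake would be the reading that SEP itself drives the difference, and the section 7.7 analysis of why, which a significant interaction triggers.

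**Working it through.** **The plan's own figure.** Inputs from section 7.8: f = 0.1, α = 0.05, 80% power, four groups, one covariate. With a noncentral F, one numerator degree of freedom and λ = N·f², the smallest N is 787, or 788 for four equal groups. Power at 788 is 80.1%. The stated 788 reproduces.

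**What the planned test does if only age moderates.** Code labelling L as ±1, and standardise age A and education E with correlation r. Suppose y = g·L·A + error with unit error SD, so that education has no role of its own. Because the mean of A at a given E is r·E, the labelling effect at education level E is 2·g·r·E. The education interaction is then f = g·r, and λ = 788·(g·r)². Neither g nor r is in the documents, so both are assumed.

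| Age moderation g | \|r\| = 0.2 | \|r\| = 0.3 | \|r\| = 0.4 |
|---|---|---|---|
| 0.10 | 8.7% | 13.4% | 20.2% |
| 0.05 | 5.9% | 7.05% | 8.7% |
| 0.04 | 5.6% | 6.3% | 7.3% |
| 0 | 5% | 5% | 5% |

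For example, g = 0.1 and r = 0.3 give λ = 788 × 0.03² = 0.709 and rejection in 13.4% of trials. Simulation (8,000 runs per setting) gives 8.5, 13.5 and 20.5% for the first row. With age and its two products in the model the rates are 5.4, 5.4 and 4.8%.

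**Whether these are errors.** The null hypothesis of the planned test is that the labelling effect is the same at every education level. In the example that is false. The effect is 2 × 0.1 × 0.3 × E = 0.06·E, so people one SD above and one SD below mean education differ in their labelling effect by 0.12 residual SD. Rejecting is correct for the question in section 2. The age-adjusted model returns a mean education interaction of zero in the same scenario, because it compares people of equal age. That is a different question from whether the groups, as they exist, respond differently.

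**How large the assumed input is.** Section 7.8 reports two previous main effects on energy density: f = 0.14 for default order and f = 0.04, not significant, for swaps. These were different interventions, but age moderation of f = 0.1 is large beside them, and it equals the education interaction for which the trial is powered.

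**Mediation.** Take the correlations in 7.8 (education with motive 0.17, motive with outcome −0.25), an assumed age–motive correlation of 0.2, age moderation of f = 0.1, and no motive × labelling effect. Then 5.0, 5.2 and 5.1% of triggered analyses have a 99% interval for the difference in indirect effects that excludes zero. Multiplied by the trigger rates:

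- 0.087 × 0.050 = 0.4%
- 0.134 × 0.052 = 0.7%
- 0.202 × 0.051 = 1.0%

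Over all trials this is about the 1% level that section 7 sets for secondary analyses. With 95% intervals the triggered rates are 14.5, 15.8 and 14.7%, or 1.3, 2.1 and 3.0% of all trials, below 5%.

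**What an age-adjusted model would deliver.** The chance SD of the shift in the education estimate on adding age is r/√(788·(1 − r²)) = 0.007, 0.011 and 0.016. At g = 0.05 the expected shift g·r is 0.010, 0.015 and 0.020, or 1.3 to 1.4 SD. It exceeds 1.96 SD in only 28, 27 and 25% of trials. At g = 0.1 the figures are 79, 76 and 73%. When the education interaction is real and age plays no part, 4, 7 and 12% of significant primary results lose significance in the adjusted model. Section 7.6 reports sensitivity results by changes in significance, so the model would also need an exception to that rule.

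**The case for a change.** The strongest case is that the plan goes beyond description. Its hypothesis says that SEP will influence the effects, its secondary objective is to explain why, and a significant interaction opens the mediation analysis. On that explanatory reading, an interaction that runs through age would mislead. Specifying the check in advance avoids choosing covariates after seeing the data, and the primary test would stay as it is.

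Much of this stands as fact. No described model contains age, age has no quota, the figures above reproduce, and an interaction with a non-randomised variable is observational. Given that the mediation is triggered, its false-positive rate of about 5% is above 1%; including age and age × labelling brings it to between 1.2 and 2.6%. At an assumed age–motive correlation of 0.3 it is 7 to 10% of triggered analyses, or about 1 to 2% of all trials.

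It does not make the plan wrong. The objective sets the estimand as a difference between SEP groups, and nowhere does the plan claim an education effect independent of age. Nor is age the only variable that fits the selection argument: ethnicity is collected (Appendix E, item 3), has no quota, is not a consequence of education and is not an SEP measure. The gender quota is not stated to hold within education level either. Calling the interaction observational is a matter for the results report.

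**Conclusion.** The concern does not hold. Followed as written, the plan gives a valid answer to its primary question, and the main effects are protected by randomisation. The rejection rates of 8.7 to 20.2% are power against a true difference by education, not false positives. They rest on an age–education correlation of 0.2 to 0.4 and age moderation of f = 0.1, neither of which the documents supply. The rates are 5.9 to 8.7% at f = 0.05 and 5% if either input is zero. The possible effect on mediation is about 0.4 to 1.0% of all trials at the 1% level, and about 1 to 2% under the stronger assumption on the age–motive correlation. A model with age is a reasonable optional extra that a careful statistician could equally decline. The conclusion would change only if the trial claimed that education modifies the effects independently of age.
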